10.0 Data and Specimen Banking

N/A

11.0 Data Analysis/Management

We will conduct intent-to-treat analyses. Children will be the unit of analyses, although analyses will recognize the hierarchical nature of the data, i.e., time points nested within children, and children nested within Head Start centers. Randomization at the center level with stratification by study site should balance many observed and unobserved confounders at the center and child levels. For the primary (screen time) and other outcomes (BMI z-score, dietary energy intake, and MVPA), two sets of analyses will be performed. The first set of analysis will be separate cross-sectional analysis of T2 and T3 outcomes respectively. Given the nested structure of the data, we will apply mixed effects regression models¹⁵⁶ to examine the effects of the intervention on each outcome while controlling for unbalanced covariates and account for correlations due to clustering. In the second set of analysis we will conduct a repeated measure analysis using outcomes from all 3 time points. For Hypothesis 2, we will assess the extent through which parent outcome expectations, self-efficacy, and screen time parenting practices exert their influence on (i.e., mediate) change in screen time via the intervention. We will use a structural equation modeling (SEM) approach^{157,158} specifically, we will evaluate mediation by decomposing a total effect on the screen time slope into direct effects and indirect effects. The indirect effects represent the influence of the intervention on change in screen time via parent outcome expectations, self-efficacy, or screen time parenting practices. We will test the moderation relationships of Hypothesis 3 using mixed effects regression models as outlined for Hypothesis #1.

Power Analysis. With only two post-intervention assessments, there is limited information on trajectories of outcomes over time. Thus, our primary analysis will focus on comparisons at Time 2 (post 1) and Time 3 (post 2), respectively. We evaluated the statistical power and sample size for the proposed study using the Optimal Design Software.¹⁶⁸ Parameter estimates saved from a pilot data analysis^{33,40} were used for population parameter values for data generation and coverage. We assumed an increasing attrition rate over time reflecting the likelihood that participants may drop out of the study (~15% overall); therefore if we power the study with 240 participants at Time 3, we would expect to start with approximately n=280 participants at Time 1 with attrition.

Data Management:

Each study site will be responsible for managing the data collected at that site. All staff will be informed of the need for confidentiality. All key personnel at all sites will have completed Human Subjects training and all investigators and clinical trial staff will have up to date Good Clinical Practice (GCP) training. Data containing personal information such as names, addresses, and phone numbers will be maintained in a separate locked cabinet accessible only by the study coordinator and research manager. Security access only will be permitted to each file, separately, with security limited to the projects' data manager and coordinator. Personal identification codes will be created for each participant, which can link quantitative or survey data back to an individuals' name. Data will be stored on encrypted computers and servers that are protected with passwords. All data analyses will be conducted on datasets that include only the personal identification code as a linking variable. No names or addresses will be reported in publications. Only the PIs, co-investigators, research coordinator, and research administrator have keys to the offices and locked cabinets at Seattle Children's. The semi-structured qualitative interview data will have no personally identifying information associated with the tape or the transcript, so confidentiality cannot be violated.

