9.0 Procedures Involved

9.1 **Study design:** The implementation of the intervention will be accomplished in four separate waves of intervention and control centers. In year 1, [name] will enroll two Head Start centers in the Seattle-metro area for assessments and to be randomly assigned to the intervention or control condition. In each of years 2-4, Drs. [name], [name], and [name] will each enroll two Head Start centers in their respective regions for assessments and randomization to the intervention or control condition.

The intervention schools will integrate the culturally adapted Fit 5 Kids curriculum into their standard preschool day, which may be in person or remote based on how the school educating their students and how they recommend fitting the curriculum into their program. Research staff members will be trained as interventionists to teach Fit 5 Kids by [name], the interventionist from the pilot Fit 5 Kids RCT (consultant, see letter of support). The interventionists may implement the curriculum at the head start center or develop videos for parents to share with their students. Interventionists will undergo the teacher training program developed by [name] and [name] for the pilot Fit5Kids study. Training will consist of:

1. 1-week in person training led by [name] and [name] and
2. Ongoing supervision of the interventionists by [name] and [name].

The in person training will occur prior to each region's implementation of the Fit 5 Kids curriculum, i.e., for the Seattle-based interventionist at the beginning of year 1 and for the Central Valley and Houston-based interventionists at the beginning of year 2. The in person training will provide: an overview of the Fit 5 Kids curriculum, discussion of the implementation of lessons, observation of selected lessons as taught by [name], and practice teaching opportunities of selected lessons by interventionists with feedback from [name] and [name]. Key portions of these trainings will be video-recorded (staff only) and available for review by the interventionists throughout the study. Following the in person training, [name], [name], and the co-investigators, will hold joint monthly videoconferences/telephone meetings with the interventionists, to support their teaching efforts

and answer any questions that may arise. [name], [name], and the co-investigators will also be available to the interventionists by email or telephone call should the need arise.

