19. Moderator: Maternal social support. While parental stress may adversely affect parenting behaviors and lead to greater screen time, social support is thought to moderate the impact of parental stress on parenting behaviors and health outcomes, i.e., Cohen's stress-buffering hypothesis.¹⁴⁹ For example in a study of low income preschoolers, social support measured by the Multidimensional Scale of Perceived Social Support moderated the adverse association between higher parental stress and higher preschoolers' screen time.¹⁵⁰ In a study of Head Start preschoolers, greater social support

measured by the Multidimensional Scale of Perceived Social Support was associated with parents highly restricting their preschoolers' screen time.¹⁵¹ We will use the validated 12-item Multidimensional Scale of Perceived Social Support.^{152,153} This scale measures perceived support from family, friends, and a significant other, and respondents rate this on a 7-point Likert scale. The total score for social support will be a potential moderator in analyses estimating screen time, with the hypothesis that the Fit 5 Kids intervention will have greater efficacy for reducing screen time among preschoolers of mothers with higher social support.

20. Covariates: Socio-demographics. Parents will complete a survey on their child's age, sex, race/ethnicity, parent education, and household income. Previous studies^{40,154} have reported socio-demographics as important predictors of Latino children's screen time, physical activity, and/or BMI z-score.

21. Covariate: Perceptions of neighborhood disorder. We will use an 8-item,¹¹⁴ validated neighborhood disorder scale to assess parents' perceptions of their neighborhood in terms of safety, violence, drug traffic, and child victimization.¹¹⁵ The scale showed acceptable internal consistency (Cronbach's alpha=0.95), reliability (generalizability coefficient=0.84), and validity comparing various neighborhoods ($p<0.001$).¹¹⁵ In previous work led by [name] using this scale, neighborhood disorder was a significant correlate of Latino Head Start preschoolers' PA and adiposity (see Preliminary Studies).^{41,42} Total score will be a covariate.

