20.0 Setting

We will recruit Head Start centers in three different regions of the US, in order to increase generalizability of study findings, as well as to be inclusive of the most underserved of Latino groups, i.e., rural Latinos. We will recruit 8 Head Start centers in the Seattle-metro area, which include urban and suburban-based centers. We will recruit 6 centers from the rural Central Valley of Washington State. We will also recruit 6 centers from the Houston-metro area, which include urban-based centers.

The Puget Sound Educational Services District (PSESD) is a state mandated educational services district in Washington State. PSESD operates 26 Head Start centers throughout the Seattle-metro area which enroll 863 Latino preschoolers. PSESD has agreed to partner with the investigators (see letter of support from [name]). In the rural Central Valley of Washington State, Inspire Centers operates 28 Head Start centers serving over 600 Latino preschoolers and will participate in this study (see letter of support from [name]). In

Houston, AVANCE, Inc. operates 13 Head Start centers that serve 920 Latino preschoolers and has expressed a desire to participate in this study (see letter of support from [name]).

Research staff will recruit participants from these Head Start centers. Other Head Start centers will also be invited to participate, including Denise Louie Education Centers (based in Seattle, WA) and Educational Opportunities for Children and Families (based in Vancouver, WA). Seattle Children's investigators will be conducting/overseeing the research procedures at the Head Start centers and the investigators will be acting as agents of Seattle Children's at those sites. Participants will also complete some of the study components on their own at their home.

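### Centers are randomized within study site, but the primary Time 2 and Time 3 models name no site term, so the standard error is too large if site predicts the outcome.

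*Combined protocol and SAP*

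**What the plan says.** Section 11.0 describes allocation of Head Start centers stratified by study site: "Randomization at the center level with stratification by study site should balance many observed and unobserved confounders at the center and child levels". The only nesting it names is time points within children and children within centers. The mixed models estimate the intervention effect "while controlling for unbalanced covariates and account for correlations due to clustering". The power paragraph of the same section settles which analysis leads: "our primary analysis will focus on comparisons at Time 2 (post 1) and Time 3 (post 2), respectively".

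Site does not appear in Section 11.0 as a fixed effect, a random effect or a covariate, and Table 1 in Section 9.0 does not list it. Section 9.0 does name other covariates that may differ by region, among them parent acculturation and perceived neighborhood disorder ("Total score will be a covariate"). The waiver text in Section 30.0 adds home location and neighborhood details as an analysis factor.

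On the strata, Section 20.0 states "We will recruit 8 Head Start centers in the Seattle-metro area" and "We will recruit 6 centers from the rural Central Valley of Washington State", with 6 more centers in the Houston metro area. Section 9.1 says that in years 2 to 4 the three regional investigators "will each enroll two Head Start centers in their respective regions for assessments and randomization to the intervention or control condition". That implies, but does not state, one center per arm in each site-year.

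**The concern.** When allocation is balanced within strata, differences between strata drop out of the arm comparison. The true sampling variance of the estimate therefore does not contain them. A model that ignores the strata still counts them as between-center noise, so its standard error exceeds the real one if the stratum predicts the outcome.

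Here the strata are two metropolitan regions and one rural region, so a site difference in screen time, BMI z-score, diet or activity is plausible. With about 20 clusters there is little precision to spare. The only adjustment rule in the plan selects on imbalance, which is the wrong criterion for a factor that was balanced by design and may still be prognostic.

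**Working it through.** **The plan's own figure.** The plan expects 240 children at Time 3 and about 15% attrition. 240 / (1 − 0.15) = 282.4, rounded up to 283, against about 280 stated; the figure reproduces within rounding. The power behind the 240 cannot be reproduced, because the text gives no alpha, effect size, SD, ICC or between-site variance.

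**Inputs from the documents.** 240 children at Time 3 and 8 + 6 + 6 = 20 centers (Section 20.0; Section 9.1 also gives 2 + 3 × 3 × 2 = 20), so 240 / 20 = 12 per center.

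**Assumed, not in the documents.** Two-sided 5% test; residual ICC 0.05 on a within-site child variance of 1; effect 0.5 SD; arms split 4/4, 3/3 and 3/3 within site; equal center sizes; three independent site effects with SD τ.

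**Step 1: true standard error.** Variance of a center mean within site: v = 0.05 + 0.95/12 = 0.1292. With 10 centers per arm, the SE of the arm difference is √(2v/10) = √0.0258 = 0.161. This does not depend on τ, because site cancels.

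**Step 2: standard error without a site term.** The between-center mean square on 18 df has expectation v + τ² × [20 − (8² + 6² + 6²)/20]/18 = v + τ² × 13.2/18 = v + 0.733τ².
- τ = 0.1: 0.1292 + 0.0073 = 0.1365, SE √(0.1365/5) = 0.165, about 3% too large.
- τ = 0.2: 0.1292 + 0.0293 = 0.1585, SE √(0.1585/5) = 0.178, about 11% too large.

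**Step 3: power.** Noncentrality is 0.5/0.161 = 3.11. The exact noncentral t gives 83.7% on 18 df (critical value 2.10) with no site effect and no site term. With the site term it gives 83.1% on 16 df (critical value 2.12), at any τ. The other entries come from simulated center means.

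| Site SD | Power, no site term | Power, site term | Type I, no term / term | Mean CI half-width, no term / term |
|---|---|---|---|---|
| 0 | 83.7% | 83.1% | 5.0% / 5.0% | about equal |
| 0.1 | 82.3% | 83.1% | 4.5% / 5.0% | 0.342 / 0.335 |
| 0.2 | 77.7% | 83.1% | 3.4% / 5.0% | 0.368 / 0.335 |

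Break-even is near a site SD of 0.06. Put as a plain contrast, if one 6-center region differs from the others by 0.2 SD, power without the term is 81.9%; at 0.3 SD it is 79.5%.

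**Step 4: sensitivity.**
- Over residual ICC 0.02 to 0.10 and effect 0.4 to 0.6 SD, the gain from the term is −0.6 to −0.2 points at site SD 0, +0.3 to +1.7 at 0.1, and +2.2 to +8.5 at 0.2.
- With 22 centers (10/6/6) the gain is −0.4, +0.9 and +4.8 points at site SD 0, 0.1 and 0.2.
- If listed covariates absorb half the site variance, the gain is +0.2 at 0.1 and +2.5 at 0.2.
- A second parameterization sets the effect to give 80% power with site in the model, takes ICC 0.01 or 0.05, and fixes the site variance across centers. Without the term the SE is 1.04 to 1.06 times the adjusted one at site variance 0.01 (power 77–78%), and 1.09 to 1.12 times at 0.02 (power 74–75%).

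**The case against.** The strongest reply is that the loss is small and unanchored. The ICC, effect size and site SD are all assumed. At site SD 0.1 the gain is about one point, and the larger figure at 0.2 needs site to supply 0.04 of a total between-center variance of 0.09, or 44%. Nothing in the documents supports a value that high. This stands as a limit on size.

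Second, outcomes are also measured at Time 1. Section 11.0 does not name baseline adjustment for the Time 2 and Time 3 models, but if the baseline value were used it would remove much of a stable site difference. Under one set of assumptions (child-level baseline slope and correlation 0.5, effect rescaled to 0.37 SD for similar power) the gain falls to about 0.2 points at SD 0.1 and about 2 points at 0.2. This also stands, and agrees with the half-absorption case above.

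Third, stratification balances centers, not children. Unequal center sizes and attrition could leave site shares unequal between arms, and the imbalance rule might then admit site. That is possible, but inclusion would depend on the observed data, which is a reason to fix the term by design. Exact cancellation does rest on the assumed equal centers and even splits.

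Fourth, a site term judged against a normal reference is not safe. At site SD 0.2, type I error is about 4.5–4.7% without the term and 6.7–6.9% with it. Section 11.0 names no df method. The point is correct, so the term and a small-sample df method belong together. The term does not create the problem: at site SD 0 the normal reference already gives about 6.6% without it.

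**Conclusion.** The concern holds. As written, the primary models leave out the factor on which centers were stratified, and no other section brings it in. If site is prognostic, the Time 2 and Time 3 standard errors are overstated and the tests are conservative; estimates are not biased and false positives are not inflated.

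Under the base assumptions the SE is about 3% too large at site SD 0.1 and 11% at 0.2, costing about 1 and 5 to 6 points of power. If site does not matter, or baseline and other covariates absorb most of it, almost nothing is lost. The planned repeated-measures analysis is less affected, since stable site differences cancel from within-child change. The conflicting center counts (22 in Section 3.0, 20 in Section 20.0, 10 for Seattle in Section 26.0) do not alter the direction.

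**What to change.** - Name study site as a fixed effect in the Time 2 and Time 3 models, whatever the observed balance, and in the repeated-measures model for consistency.
- Define site as the stratum used at randomization. Section 20.0 also invites a provider outside the three named regions ("Educational Opportunities for Children and Families (based in Vancouver, WA"), so say which stratum holds any of its centers.
- Test the arm effect with Kenward-Roger or Satterthwaite degrees of freedom based on centers.
- State whether the two centers of each site-year were split one per arm. Add school year as a fixed effect only if the randomization record confirms that. It uses 3 more df, costing about 1 further point if pairs were split, but about 7 to 10 points at site and wave SDs of 0 to 0.1 if only site was balanced.
- Section 30.0 says participation is complete and the study is open for analysis. If results by arm are already known, label the site-adjusted model as not prespecified and report it beside the model as written.

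The cost is a few lines of SAP text and no new data, since each child's site follows from the center. The site term takes 2 of about 18 between-center df, or about half a power point if site has no effect.

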8. Facebook – Similar process. However, we will further utilize Facebook as a platform to distribute video lessons to participants, post the newsletters, post pictures of the activities being mailed home, share information for attending the digital lives, and post the parent engagement questions from the goal setting form as another way to gauge their engagement in the remote intervention. This content will also be available to participants outside of Facebook.
9. Booster Weeks – If booster weeks are done remotely, we will follow similar procedures as outlined above. Like the in-person version of the booster weeks, parents will still receive a newsletter and text message tip daily (for each lesson). There will be 5 video booster lessons, and we will mail home activities for 4/5 of them. Parents will be invited to attend an optional Digital Live. We will set goals once for the booster week(s) period, and will still post the same type of content on Facebook.

Control condition: The control centers will not implement Fit 5 Kids but will instead provide their children with the standard Head Start preschool curriculum. This standard curriculum typically provides brief advice on healthy eating and active living, but does not go into detail about screen time reduction. As this is the standard practice of Head Start programs, there are no ethical issues to consider with the control participants.

Measurement Procedures. The investigators have experience with all proposed questionnaires and accelerometry among Latino families, ensuring high scientific rigor. All assessments and surveys measuring mediating, moderating and outcome variables as well as covariates will be assessed immediately pre-intervention (Time 1, i.e., September/October of each year), immediately after the classroom intervention (Time 2, i.e., January of each year), and 8-months after starting the

intervention (Time 3, i.e., May/June of each year). The Time 2 measurement is necessary in order to detect changes in mediators (e.g., parenting practices and parent self-efficacy) that will be expected to change prior to outcomes such as BMI z-score. The Time 2 measurement will allow for mediation analyses to better describe mechanisms underlying changes in outcomes.⁹⁸ The dietary assessment by Food Frequency Screener will occur at Time 1, Time 2, and Time 3. Research staff will collect socio-demographic and anthropometric measurements on the children and parents at their assigned Head Start center.

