age.^{41,42,103,104,140,141} Accelerometers will be delivered to and picked up from participants at the Head Start centers with the option of postage-paid mailings directly to/from their homes. The accelerometer data quality standards by Troiano et al,⁴⁸ used by [name] and others,^{104,140-142} will be used also including criteria for: non-wear and wear time (non-wear time defined as 60 consecutive minutes of zero accelerometer counts, except for 1-2 minutes of counts between 0-100, and wear time defined by subtracting non-wear time from 24 hours).⁴⁸ We will use the MVPA (420 counts/15 seconds) and sedentary cutpoints (37.5 counts/15 seconds) validated in preschoolers by Pate and colleagues.⁵⁷ At least 5-valid days of accelerometer data with three or more hours of wear time will be used in analyses to estimate habitual PA, because those criteria provided >70% reliability among preschoolers.^{143,144} To maximize valid accelerometer data, participants will wear accelerometers for 24 hours/day, except for water-based activities,¹⁴⁵ and re-wear them for another 7-day period if they have less than 5-valid days of data at each measurement time point. This approach yielded 92.5% of participants from the analytic sample with sufficient valid accelerometer data in the pilot Fit 5 Kids cluster RCT.⁴⁰ Valid accelerometer wear time will be a covariate for analyses involving accelerometer data. The accelerometers will be provided at no cost by [name].

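### The primary Time 2 and Time 3 models have no fixed baseline (Time 1) term: baseline screen time may never enter, or may enter only through an undefined judgement of imbalance, so precision may be partly or wholly lost

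*Combined protocol and SAP*

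**What the plan says.** Section 11.0 (Data Analysis/Management) describes two sets of analyses for screen time and the other outcomes. On the first: "The first set of analysis will be separate cross-sectional analysis of T2 and T3 outcomes respectively". These are mixed effects models meant "to examine the effects of the intervention on each outcome while controlling for unbalanced covariates and account for correlations due to clustering". On the second: "In the second set of analysis we will conduct a repeated measure analysis using outcomes from all 3 time points". The power paragraph of the same section then ranks them: "our primary analysis will focus on comparisons at Time 2 (post 1) and Time 3 (post 2), respectively". Its reason is that two follow-up visits say little about the shape of change.

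Baseline screen time is available. Section 9.0 (Measurement Procedures) states that "outcome variables as well as covariates will be assessed immediately pre-intervention (Time 1, i.e., September/October of each year", and again at Times 2 and 3. Table 1 types screen time as the primary outcome. The covariate label goes to socio-demographics, neighborhood perceptions, acculturation and the COVID-19 questionnaire. For accelerometer outcomes section 9.0 adds: "Valid accelerometer wear time will be a covariate for analyses involving accelerometer data". None of these carries a balance condition there, and section 11.0 does not say whether they always enter or enter only when unbalanced. Section 11.0 also refers to "Randomization at the center level with stratification by study site", but does not say that site is in the model.

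**The concern.** Two things are left open in the primary model. First, the baseline value of the outcome is often a strong predictor of the follow-up value, and no text makes it a fixed term. Either it stays out, or it enters when someone judges it unbalanced. Adjustment for a prognostic baseline improves precision even when the arms are perfectly balanced, so observed imbalance is the wrong trigger. Second, with no test, threshold or candidate list, the primary covariate set can be settled after the data are seen.

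The stated reason for preferring separate visits does not require leaving Time 1 out. A Time 2 or Time 3 contrast can be adjusted for Time 1, or read from a model with time as a category, without modelling a trajectory.

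**Working it through.** **The plan's own figure.** 240 children at Time 3 with about 15% attrition: 240/(1 - 0.15) = 282.4, so 283 enrolled against the stated approximate 280 (280 × 0.85 = 238). This is consistent. Power cannot be reproduced: section 11.0 relies on "Parameter estimates saved from a pilot data analysis" without giving the values.

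**Inputs from the documents.** 240 children at Time 3 (11.0). 20 centers from 8 + 6 + 6 (20.0); section 3.0 says 22. With J = 20 centers, m = 240/20 = 12 children per center.

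**Assumed inputs.** ICC 0.03, 0.05 and 0.10; effect 0.40 SD; correlation r between Time 1 and follow-up of 0.3 to 0.7; two-sided 5%; noncentral t with 20 - 2 = 18 df.

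**Formulas** (variance of the arm difference in SD units):
- Unadjusted: V0 = (4/J)[ICC + (1 - ICC)/m]
- A, baseline explains both levels: V0(1 - r²)
- B, child level only, baseline centered within center: (4/J)[ICC + (1 - ICC)(1 - r²)/m]
- C, child level only, uncentered: (4/J)[ICC(1 + r²) + (1 - ICC)(1 - r²)/m]

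At ICC 0.03, V0 = 0.2 × (0.03 + 0.97/12) = 0.0222 and SE = 0.149; unadjusted power is 72%. Under A the variance falls by r², that is by 9%, 25%, 36% and 49% at r = 0.3, 0.5, 0.6 and 0.7.

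| ICC 0.03 | r = 0.3 | 0.5 | 0.6 | 0.7 |
|---|---|---|---|---|
| A, both levels | 76% | 84% | 89% | 95% |
| B, child only, centered | 75% | 80% | 84% | 89% |
| C, child only, uncentered | 74% | 77% | 79% | 82% |

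Under A, the effect detectable with 80% power falls from 0.44 SD to 0.42, 0.38, 0.35 and 0.32 SD. With 22 centers the picture is the same: 73.5% unadjusted and 77%, 85%, 90% and 95% adjusted.

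**Less favourable ICCs, case C.** At ICC 0.05, unadjusted power is 65% and the change is +0.9, +2.5 and +5.1 points at r = 0.3, 0.5 and 0.7. At ICC 0.10, unadjusted power is 53% and the change is -0.5, -1.4 and -2.7 points. Setting C equal to V0 gives ICC = (1 - ICC)/m, so the gain vanishes at ICC = 1/(m + 1) = 1/13 = 0.077. Case B cannot lose in this way, because centering keeps center-level noise in baseline out of the contrast.

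**Conditional entry.** Simulation on center means under assumption A (ICC 0.03, effect 0.40 SD, 100,000 simulated trials per r):

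| Rule for entering Time 1 | Enters in | Power, r = 0.5 | Power, r = 0.7 | Share of power gain kept |
|---|---|---|---|---|
| Never | 0% | 72% | 72% | 0 |
| Baseline p < 0.05 | 5% | 73% | 74% | about 8% |
| Standardized difference > 0.25 | about 9% | 74% | 75% | about 15% |
| Standardized difference > 0.1 | 50% | 79% | 86% | about 60% |
| Always | 100% | 83% | 95% | 100% |

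Under the last conditional rule about 93% of the sampling-variance gain is kept but only about 60% of the power gain, because half the trials still use the larger unadjusted standard error. In a child-level simulation with no effect, type I error of the three conditional rules lay between 3% and 5%.

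**The case against.** **The plan does use baseline.** The repeated-measures set covers all three visits and applies to the primary outcome, and only the power paragraph ranks the two sets. This stands: a reader might infer that the plan ignores baseline, and the documents do not support that. The gap concerns the models named as the primary focus.

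**Baseline may yet enter the primary models.** That Time 1 is definitely excluded is also too strong. The measurement schedule lists outcomes and covariates separately, but a schedule does not settle what a model contains. The text permits both readings, and neither makes baseline a fixed term.

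**Randomization makes the unadjusted comparison valid.** Correct. A reader might infer bias or inflated type I error. Neither follows: with a rule set in advance, the simulated conditional rules were at or below 5%.

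**The gain may be small or negative.** This stands. The largest figures assume that baseline explains center variance as well as child variance. Case C is extreme, since it assumes no center-level correlation at all, but it shows that a raw, uncentered Time 1 term is not a safe remedy at every ICC.

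**The design may leave fewer degrees of freedom.** Section 9.1 has each site enroll two centers a year for randomization, which suggests pairs. With 10 pairs (9 df) and the same variance, unadjusted power at ICC 0.03 would be 67%, not 72%. The levels would shift; the reason to fix the covariates would not.

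**Conclusion.** The point holds as a matter of efficiency and pre-specification. It needs no assumption to say that section 11.0 has no fixed Time 1 term and no criterion for imbalance. The plan is valid if the rule is fixed in advance, but some or all of the precision from fixed adjustment may be lost, and the covariate set of the primary models is open until someone closes it.

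It would go too far to say that all the precision is lost: conditional entry keeps between about 8% and 60% of the power gain, depending on the criterion. The size is conditional throughout. Under the assumptions stated, fixed adjustment ranges from a gain of about 22 points of power (r = 0.7, both levels, ICC 0.03) to a loss of about 3 (r = 0.7, child level only, uncentered, ICC 0.10). Confidence is high on the gap in the text and limited on the size. The change is worth making because it uses data already collected.

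**What to change.** In section 11.0, replace the control for unbalanced covariates with a fixed rule. Every Time 2 and Time 3 model includes, whatever the observed balance:
- the Time 1 value of that outcome, as the child's deviation from the center mean, with the center mean as a second term if degrees of freedom allow (the second term is what captures any center-level gain);
- the study-site stratum by which centers were randomized.

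State also whether the covariates listed in section 9.0 always enter.

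Alternatively, read the Time 2 and Time 3 contrasts from the already planned three-time-point model, with time as a category and baseline means constrained equal across arms.

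**Cost.** No new data. Missing Time 1 values must be handled: the adjusted model drops children without Time 1 unless it is imputed, while the three-time-point model keeps them. A few center-level degrees of freedom are used: two for three sites and one for the center mean would leave 15 of 18.

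**Timing.** Section 30.0 says participants have finished and the study is open for analysis only. Date the change and state whether outcomes by arm had been seen. If they had, report the adjusted result as post hoc beside the planned one.
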